### 3.0 Inclusion and Exclusion Criteria

Table 1. Inclusion and Exclusion Criteria	
Eligibility Criteria:	Exclusion Criteria:

1. ≥ 18 years of age

2. Self-identify as Black, Hispanic, American Indian, or NLW

3. Clinically significant anxiety and/or depressive symptoms as evinced by a score of 8 or higher on the Overall Anxiety Severity and Impairment Scale (OASIS) and/or Overall Depression Severity and Impairment Scale (ODSIS)

4. Reside in the United States

	

1. Not fluent in English

2. Lifetime or significant cognitive impairment

**FULL PROTOCOL TITLE:** Mobile Health to Monitor Risk for COVID-19 and Improve Mental Health during the Pandemic

5. Willing/able to complete EMAs on study provided or personal smartphone for 6-month study period 6. Willing and able to complete the 3- and 6-month follow-up assessments via Insight™ app and over the phone (i.e., qualitative interview) 7. Score $\geq 4$ on the REALM-SF indicating > 6th grade English literacy level (needed to complete EMAs)	4. Identifying as a race/ethnicity for which the corresponding study cell has been filled
---	---

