## 8.0 Study Timelines

The present study will include a baseline assessment, a 3-month intervention period, a 3-month continued assessment period (with access to intervention materials), and 3- and 6-month post-baseline assessments that includes a qualitative interview for selected participants via phone or online platform (e.g., Zoom). The qualitative interviews will be recorded and securely stored for qualitative analysis (or completed by the participant via REDCap survey if a medical condition prevents them from being able to speak for long periods of time). Recordings will be transcribed by internal staff, Microsoft Transcribe, or by approved contractors. When using Microsoft Transcribe, all transcriptions will be reviewed by study staff. Hence, the total duration of an individual subject's participation in the study will be 6 months. We expect each study appointment will take approximately 30-60 minutes to complete.

Baseline timeline: All study assessments as well as all EMAs will be conducted remotely through the Insight app. Participants who do not have a mobile phone will be mailed one. The Insight™ app will be downloaded and activated during the baseline session using a unique activation code provided by the research team. All interactions with the Insight and EASE app will be date, time, and Geolocation (GPS) stamped and app feature use will be recorded for future analysis. After downloading the Insight app, participants will use the app to complete the baseline assessment. We expect participants will take approximately 30-minutes to complete all baseline assessment measures (please refer to section 10.0 procedures involved for a detailed list of measures participants will be prompted to complete). Following completion of the baseline assessment, the

**FULL PROTOCOL TITLE:** Mobile Health to Monitor Risk for COVID-19 and Improve Mental Health during the Pandemic

app will request a code. This code will be used to ensure that the participant is placed in their randomly assigned study condition (EASE or Control). Upon entering this code, the app will automatically begin prompting twice daily EMAs for 6-months (please refer to section 10 below and Table 3 for a list of EMA assessments and more detailed information).

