COVID-19 Psychological Impact Survey	3		3	3	OASIS (5)
Daily Activities (A.1: H.1)	3		3	3	SSASI (5)
Change in Fast Food Consumption during COVID-19	1		1	1	PSI (8)
COVID-19 Substance Use (A.3.b)	4		4	4	ODSIS (5)
AUDIT-C	3		3	3	Report Distress
Marijuana/Cannabis Use Behavior	6		6	6	Affect (15)
Abbreviated Multidimensional Acculturation Scale (A.2)	15		15	15	Location
LEC5 & PCPTSD-5	6		6	6	Pain Level Ability to Cope with Stress
Three-item Loneliness Scale	3		3	3	
Mindful Attention Awareness Scale (MAAS)	15		15	15	Report COVID-19 Symptoms
Total items	273	54	209	188	Current Symptoms Exposure to someone with COVID Loss of taste/sense of smell

Note. Screen = REDCap or Phone Screener; Base = Baseline; 3- and 6-Month FU = 3- and 6-Month Post-Baseline Follow-up. \*Indicates items that are only collected during the morning EMA. \*\*Indicates items that are only collected during the evening EMA. Please see EMA types below for more information.

**EASE App Features and Treatment Components.** See Table 2 for app components. EASE offers

**Table 2.** Comparison of EASE and Control conditions

App Components	EASE	Control
EMA	X	X (add on for this study)
COVID-19 monitoring and intervention	X	X (add on for this study)
AS psychoeducation	X	
On demand tips and exercises		
Coping with mood	X	X
Coping with stress	X	X
Interoceptive exposure	X	
Guided relaxation	X	X
Inspirational messages	X	
Challenge Automatic	X	

**FULL PROTOCOL TITLE:** Mobile Health to Monitor Risk for COVID-19 and Improve Mental Health during the Pandemic

clinical grade care by integrating standard CBT with a transdiagnostic treatment for AS reduction. Individuals randomized to the EASE group will receive: 1) scheduled treatment, 2) scheduled and cued interoceptive exposure sessions, 3) on-demand intervention content (i.e., how to cope with symptoms of anxiety and depression; cognitive restructuring exercises; guided relaxation videos), and 4) tailored treatment messages based on responses to EMA items. Information about frequency of resource use and length of time spent viewing EASE intervention content will be collected through Insight™.

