Data analysis overview: Hypotheses for Aims 1 and 2 will be examined using latent growth models (LGM), multilevel structural equation models (MSEM) and latent difference score models using MPlus 8.0. To simplify subsequent sections, an overview of the common data analysis elements is presented first. Data will first be examined for multivariate normality and outliers to determine the most appropriate estimator. The maximum likelihood (ML) estimator will be used if data are approximately normal. Robust maximum likelihood (MLR) will be used if the data are not multivariate normal. We anticipate some participant attrition during the trial. Missing data will be handled in all analyses using direct ML techniques within MPlus under a missing at random (MAR) assumption. Modern missing data techniques such as direct ML increase statistical power and provide more accurate estimates of model parameters and standard errors and are the recommended intent-to-treat approach for clinical trials. LGM will generally be used to model outcomes collected at major assessments. MSEM will be used to further examine the longitudinal course of outcomes and hypothesized mechanisms of action as MSEM is ideally suited for disentangling within and between individual variance in order to more precisely estimate main effects, lagged effects, and indirect effects in intensive longitudinal designs. Evaluation of model fit in the LGM/MSEM models will be examined using fit diagnostics (i.e., standardized residuals) and common fit statistics (i.e., root mean square error of approximation) following the associated cutoff criteria recommended by Hu & Bentler. We will assess the equivalence of the treatment groups on key baseline

**FULL PROTOCOL TITLE:** Mobile Health to Monitor Risk for COVID-19 and Improve Mental Health during the Pandemic

variables (demographics and psychological variables); variables on which the groups differ will be used as covariates in the final analyses. We will also examine attrition from the study as a dichotomous outcome and use logistic regression to determine if treatment assignment predicts attrition.

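### As the available text reads, covariates for the Aim 1 and Aim 2 models are chosen by chance baseline differences between randomised arms; the harm is small and a fixed set is a cheap improvement

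*Combined protocol and SAP*

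**What the plan says.** The rule stands in the data analysis overview in Section 20.0, among the elements common to Aims 1 and 2, so it governs H1. It begins "We will assess the equivalence of the treatment groups on key baseline" variables, narrows these in a parenthesis to demographic and psychological ones, and concludes that "variables on which the groups differ will be used as covariates in the final analyses". No variables are listed, and no test, p-value or standardised difference defines a difference.

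On the model, the overview says "LGM will generally be used to model outcomes collected at major assessments". It does not say whether arm acts on the intercept, the slope or both.

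The overview also announces later text: "To simplify subsequent sections, an overview of the common data analysis elements is presented first". No aim-specific analysis sections appear in the available text, and nothing elsewhere in it names a covariate.

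Section 8.0 describes assignment to EASE or control as random. Race/ethnicity is a recruitment cell: Section 5.0 plans 220 participants in each of four groups, and an exclusion criterion in Section 3.0 reads "Identifying as a race/ethnicity for which the corresponding study cell has been filled".

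**The concern.** Covariates are worth including because they predict the outcome. Under correct randomisation a baseline difference between arms is chance and says nothing about prediction. The rule can bring in a variable unrelated to follow-up because it happened to be imbalanced, and leave out a prognostic one because it happened to balance.

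The model also cannot be written down in advance. Two analysts using different but reasonable readings of *key* and *differ* could fit different H1 models to the same data. At stake are pre-specification and a little precision. The outcome's own baseline is not at stake, because it is normally the first time point of the growth model.

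**Working it through.** The documents give no alpha, power, effect size, SD or figure tied to this rule, so there is no planned figure to reproduce.

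**Inputs from the documents.** 440 per arm (Section 5.0; the 420 per arm in Section 1.0 makes no material difference here). Retention 80-90% at each follow-up (Section 8.0), so 440 × 0.80 = 352 or 440 × 0.90 = 396 completers per arm. Table 3 lists 32 instruments given at baseline.

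**Inputs assumed.** Two-sided 5% test; true effect 0.2 SD at 6 months; correlation 0.5 between baseline and 6 months; *differ* meaning p<0.05; 8 candidate terms.

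**1. What the rule would flag.** With 440 per arm, p<0.05 flags a standardised difference of 1.96 × √(2/440) = 0.132 (0.135 with 420).

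**2. How often the cut-off changes the model.** For independent candidates, two cut-offs give different sets when at least one p-value falls between them.
- p<0.05 v p<0.10, 8 candidates: 1 − 0.95^8 = 34%.
- p<0.05 v p<0.20, 8 candidates: 1 − 0.85^8 = 73%.
- With 32 candidates: 1 − 0.95^32 = 81% and 1 − 0.85^32 = 99%. These are upper bounds only, since the instruments overlap and many fall outside the two named categories.

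**3. Power.** A three-wave growth model was simulated (intercept variance 0.60, slope variance 0.05, covariance −0.05, residual variance 0.40, times 0/1/2; 5,000 replicates), with covariates related equally to all three waves. It compared covariates selected by t-test at p<0.05 with the same 8 terms always included. For a multiple correlation c with the outcome, the share of residual variance explained is c²/(3(1 − c²)). Power at 352 per arm, in %:

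| c (share explained) | Arm on slope only: rule v fixed set | Arm on intercept and slope: rule v fixed set |
|---|---|---|
| 0.20 (1.4%) | 87.7 v 87.8 | 75.8 v 75.7 |
| 0.30 (3.3%) | 86.6 v 87.3 | 74.9 v 74.5 |
| 0.33 (4%) | 87.6 v 88.6 | 75.1 v 74.7 |
| 0.46 (9%) | 87.3 v 90.0 | 74.8 v 74.2 |

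The simulation standard error is about √(0.875 × 0.125/5000) = 0.5 points, so the gaps at 0.20 and 0.30 are not distinguishable from noise. At 396 per arm, slope only gives 91.2 v 92.1 (c = 0.33) and 90.5 v 93.1 (0.46); intercept and slope gives 80.6 v 80.2 and 79.4 v 79.4.

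*Formula check at 352, no covariates.* ANCOVA: SE = √(2/352 × 0.75) = 0.0653; 0.2/0.0653 − 1.96 = 1.10; power 86.5%. Change score: SE = √(2/352) = 0.0754; power 75.6%.

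*Sensitivity.* The absence of loss in the last column depends on covariates related equally to every wave, which cancel out of change. If they are instead independent of the outcome's baseline (two waves, 352 per arm), change-score power is 77.0 v 77.8 (4% explained) and 75.7 v 77.5 (9%), and ANCOVA power is 87.4 v 88.6 and 86.6 v 89.0.

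**4. Effect on the conclusion.** With 8 candidates, significance of the arm effect differs between the p<0.05 and p<0.20 rules in 1-3% of trials. Across the set-ups tried, the estimate moves by at most 0.01-0.03 SD in 95% of trials.

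**5. Type I error.** Null rejection is 4.3-5.2% at a fixed threshold. It is 5.1-6.2% if the most favourable of three thresholds (p<0.05, 0.10, 0.20) were taken afterwards.

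**The case against.** The strongest reply is that the plan is less open than it looks and that the choice hardly matters. *Key* is restricted to two categories. The overview promises further sections that may name covariates. The simulated consequences are small: nil under one form of the growth model and about 3 points at most under the other, the latter needing a covariate correlation (0.46) that no document supports. Completer counts also understate power, since direct ML uses partial data. All of this stands, and it limits the size of the point.

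It does not remove the point. Two categories without a list still cover much of the baseline battery, *differ* remains undefined, and selection on chance imbalance is the wrong principle whatever the threshold. If later sections do name covariates, this clause would conflict with them and need reconciling.

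Three stronger readings are tempting, and the documents do not support them.
- A reader might infer that the rule inflates false positives. At a fixed threshold it does not. The modest excess arises only if the threshold is picked after seeing results, and nothing in the plan proposes that.
- A reader might infer a large power loss. An ANCOVA simulation with 10 candidates, in which the outcome's own baseline is adjusted for only when imbalanced, gave 86-90% against 96% with that baseline always included. That comparison does not apply here, because a growth model already uses the baseline measurement.
- A reader might infer that no covariate set exists anywhere. The available text cannot show that.

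**Conclusion.** The point holds in limited form. On the available text, covariates for Aims 1 and 2 depend on chance arm differences in an unlisted pool judged by an unstated criterion, so the H1 model is not fixed before arm-level baseline data are examined.

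The main cost is to pre-specification: with 8 independent candidates, a choice as ordinary as p<0.05 or p<0.10 changes the covariate set in about 34% of trials. In the main simulation, power loss is nil with arm on intercept and slope, and from within noise to about 3 points with arm on slope only. The two-wave sensitivity check stays within that overall range. The effect size, correlations, number of candidates and threshold are all assumptions; the documents supply only the sample size and retention. This is a cheap improvement, not a threat to validity.

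**What to change.** Delete the clause that turns baseline variables showing an arm difference into covariates. Before arm-level data are examined, name one covariate set for all Aim 1 and Aim 2 models from prognostically plausible variables already collected, and include it whatever the observed balance. An example is race/ethnicity recruitment cell (3 terms), age, sex, income, education and baseline SSASI: 3 + 5 = 8 terms. The documents do not show which variables are prognostic, so the choice needs the investigators' judgement.

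State three further points.
- In the H2 models race/ethnicity enters as a main effect and arm interaction, not as an additional covariate.
- In Aim 2 models a variable serving as mediator or moderator keeps that role and is not also entered as a covariate.
- The modelled outcome's own baseline stays as the first growth-model time point and is not also a covariate.

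Report the baseline comparison descriptively only. If analysis sections outside the available text name covariates, reconcile this wording with them.

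The cost is a change of wording and a few degrees of freedom out of 880 participants. No new data are needed.

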## **21.0 Sharing of Results with Subjects**

Study results will not be shared with participants.

### **23.0 Additional Approvals**

N/A
